7. STUDY PROCEDURES

7.1. Study overview

A summary of study procedures is shown in **Figure 3**.

Figure 3: Schematic of study design

7.2. Recruitment and sampling

[figure not shown]
This project is embedded in MOH-led standard routine primary care services. All new or existing patients with diabetes or hypertension receiving care at the participating MOH primary care facilities will be enrolled in the DHIS2 system. Recruitment activities will be carried out that align with the routine outreach activities of each MOH health facility; these activities may include

meetings with local leaders, public posters, and brief announcements on social media platforms or the radio.

A subset of patient participants (n=10, of whom n=5 from each health district) will be recruited for questionnaire assessments and interviews. These patient participants will be purposively selected among individuals who had enrolled in the first two months of the study and had high versus low numbers of patient visits (i.e., explanatory sequential mixed methods sampling). Study fieldworkers who are not MOH employees will make an initial contact via home visit, phone calls, or encounters at MOH health facilities. Participants who express interest in this part of the study will then receive a visit by study fieldworkers to complete informed consent and interview assessments. This visit will occur in the patient's home or another convenient private location, depending on the patient's preference.

All MOH participants and members of the Technical Advisory Committee will be asked to complete a structured questionnaire. The study team will use lists of personnel participating in trainings and contacts at each health district to identify MOH participants. Members of the Technical Advisory Committee will be recruited using INCAPs local contacts and connections from prior projects with the MOH. Subsequently, a subsample of approximately 20 MOH participants will be purposively selected for semi-structured interviews based on high versus low perceptions of intervention feasibility (i.e., explanatory sequential mixed methods sampling). Mixed-methods procedural diagrams are shown in **Figure 4**.

Figure 4: Mixed-methods procedural diagram

7.3. Study visits

7.3.1. Baseline visits at primary health care facilities

At baseline, study staff will visit all participating health centers and health posts to complete a baseline needs and readiness assessment based on HEARTS monitoring guidelines and the WHO Service Availability and Readiness Assessment tool.^{22,37,52} Topics covered include population served, clinical services offered, available resources, staffing, and other topics relating to HEARTS.

7.3.2. Monthly follow-up visits at primary health care facilities

Study staff will conduct monthly follow-up visits at each primary health care facility to monitor the availability of medications and supplies, review patient registration in the DHIS system, assess implementation of collaborative care meetings, and provide support for any

implementation issues relating to HEARTS. Study fieldworkers will also maintain a field log with notes from primary health facility visits.

7.3.3. Closing interviews with diabetes patient participants

Interviews consisting of structured and semi-structured questions lasting approximately 45 minutes will be carried out with a subsample of approximately 10 patients with diabetes at the project's termination. The focus will be on diabetes, as the study team has conducted extensive interviews with hypertension patients in prior HEARTS-aligned projects. The structured portion will cover patient reported outcome measures, and the semi-structured portion will cover to acceptability and determinants of implementation (i.e., barriers and facilitators). The Tailored Implementation in Chronic Diseases (TICD) checklist will guide the semi-structured interviews.⁵³ Visits will be carried out in-person the patient's home or another convenient location. Interviews will be in Kaqchikel, Tz'utujil, or Spanish.

7.3.4. Closing interviews with MOH health workers and administrators

All MOH participants participating in the pilot will be invited to complete a structured questionnaire, focusing on feasibility (FIM instrument), sustainability (PSAT/CSAT instrument), and usability of the facility-based electronic monitoring tool (System Usability Scale). Additionally, a subsample of approximately 20 MOH staff will be purposely selected to participate in semi-structured interviews lasting approximately 45 minutes. The TICD checklist will guide the semi-structured interviews.⁵³ Interviews may be conducted in-person or virtually.

7.3.5. Technical Advisory Committee meetings

We will establish a Technical Advisory Committee to provide high-level coordination with national authorities, as recommended in the HEARTS implementation guide.²² The Technical Advisory Committee will play a critical role to provide guidance and to plan for future scale-up. Members will likely include MOH administrators at the national, departmental, and health district levels; physicians and professional nurses working in each health district, representatives of the Guatemalan PAHO office, and other stakeholders (10-15 total members). Study staff at INCAP will organize meetings every two months during the trial and a post-trial closing meeting. Meetings will be conducted virtually and will be recorded for members who cannot attend a given session. Written meeting notes also will be shared after each session.

During the meetings, study staff will present project updates for open discussion. Using an implementation mapping approach,⁵⁴ members then will discuss the implementation determinants (i.e., barriers and facilitators) that emerge during the trial, design implementation strategies to address these determinants, clarify the causal mechanisms through which implementation strategies operate, and provide feedback on a consolidated implementation package the study team creates after the trial concludes. Study staff will guide discussions of implementation strategies using different structured tools:

- The Expert Recommendations for Implementing Change (ERIC) compilation and prior mappings of ERIC to lower-middle-income countries will be used as a foundation for proposed implementation strategies.^{55,56}
- Guidance from Proctor et al. will be used to specify implementation strategies.⁵⁷
- The APEASE (acceptability, feasibility, effectiveness, cost-effectiveness, side effects or unintended consequences, safety, and equity) tool will be used to prioritize implementation strategies.⁵⁸

- Causal pathway models will be presented to link implementation strategies, mechanisms, and key implementation outcomes.^{59,60}

7.3.6. *Chart audits*

Each week, a data manager will review all new data entered into the DHIS2 system for missingness and errors. Physicians on the study team also will perform a clinical audit of at least 25% of patient visits. The physicians will use a structured checklist to rate the guideline-concordance of clinical care and adequacy of data entry.

7.4. Data collection and management

Data will be collected using different collection methods.

- Clinical data from patient participants will be entered into DHIS2 by MOH health workers who provide standard clinical care during routine visits. DHIS2 data are stored on INCAP's server, as approved by the MOH.
- Data from structured assessments will be collected electronically using a cloud-based version of REDCap hosted at INCAP. Structured assessments include health facility monitoring, chart audits, and questionnaire data from closing interviews with patients and MOH staff. Data entry and quality control checks will be performed by study staff on all structured data entered into REDCap
- Qualitative data from semi-structured interviews will be collected in the field by a trained qualitative researcher on the study team. Other qualitative data will include field notes, meeting notes, and study team reflections implementation progress and challenges.⁶¹ Qualitative data will be securely stored on the University of Michigan's institutional Dropbox account with routine back-ups to an encrypted hard drive.

8. SAMPLE SIZE CONSIDERATIONS

Primary health facilities. The sample of health facilities will include nine health posts and 2 health centers for a total 11 primary health facilities. No formal sample size calculation was performed.^{62,63} This sample of health facilities and population size of pilot health districts is consistent with recommendations in the HEARTS Implementation Guide.²²

Table 4: Semi-structured interview sample

Actor	Number ^a
Participants with diabetes	10
MOH physicians or physicians-in-training	4
MOH professional nurses	4
MOH auxiliary nurses	10
MOH administrators	2
Total	30

^aThe interview sample will be stratified by sex (target of 50% men and women by actor) and by health district (target of 50% from each health district).

Patient participants. The target sample of patient participants will be approximately 100 individuals, or 50 participants per health district. Based on the study team's prior experience, the

anticipated breakdown is n=45 patients with hypertension only, n=45 with diabetes only, and n=10 patients with both hypertension and diabetes. However, it is possible that the improved clinical services may attract a greater number of patients to MOH care than anticipated for the pilot. Of these, a subsample of 10 participants with low versus high retention levels (defined by number of clinical visits within the study time period) will be selected for semi-structured interviews at the close of the study. To improve understanding of how diabetes can be integrated into the HEARTS hypertension primary care model, we will purposely sample patient participants with diabetes.

MOH participants. The anticipated sample of MOH participants working to implement HEARTS will be approximately 50 participants. Of these, a subsample of 20 will be selected for semi-structured interviews at the close of the study using the breakdown shown in **Table 4**.

Including patient and MOH participants, a total of 30 semi-structured interviews are planned to achieve thematic saturation.^{64,65} The interview sample will be sex-stratified with a target of 50% men and women by actor. Interviews will be analyzed as they are conducted, and more may be added if saturation is not achieved.⁶⁶

9. ANALYSIS PLAN

Quantitative analysis: Questionnaire data will be analyzed using descriptive statistics. Clinical data will be analyzed using multilevel linear and logistic regression models of individual-level data adjusting for clustering of participants within primary health facilities. Sociodemographic variables such as age, sex, education level, and other characteristics may be explored in regression models if sample sizes permit. Stata will be used for quantitative analyses.

Qualitative analysis: Semi-structured interviews will be recorded and analyzed in Spanish using qualitative directed-content analysis.^{67,68} We will only transcribe recordings if the interview were undertaken in a Mayan language (Kaqchikel or Tz'utujil), in which cases professional linguists will translate and transcribe into Spanish for analysis. Constructs from the Tailored Implementation in Chronic Diseases checklist will guide qualitative coding.⁵³ Two members of the research team proficient in Spanish will independently code transcripts, and the PI will reconcile differences.

Mixed methods analysis of primary outcomes: Quantitative and qualitative findings of primary outcomes will be integrated using joint displays, which are a mixed-methods visual technique.⁶⁹ Joint displays will show quantitative data next to illuminating participant quotes. Examination of quantitative, qualitative, and mixed-methods data will permit the study team to draw meta-inferences regarding the projects' feasibility and facilitate future implementation planning.

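### The multilevel models rest on 11 facilities with no small-sample method named; normal-based intervals for facility-clustered quantities such as mean blood pressure could cover about 89–94% instead of 95%

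*Combined protocol and SAP*

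**What the plan says.** Section 9 (Analysis plan) gives the method for clinical data: "Clinical data will be analyzed using multilevel linear and logistic regression models", fitted to individual-level data and "adjusting for clustering of participants within primary health facilities". On software it says only "Stata will be used for quantitative analyses". It names no estimator (maximum likelihood or REML), reference distribution, degrees of freedom, confidence level or interval method, and no other section supplies one.

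Section 8 (Sample size considerations) fixes the clusters: "nine health posts and 2 health centers for a total 11 primary health facilities". For facilities it adds "No formal sample size calculation was performed". On patients it says "The target sample of patient participants will be approximately 100 individuals, or 50 participants per health district", split as "n=45 patients with hypertension only, n=45 with diabetes only, and n=10 patients with both hypertension and diabetes". It also warns that "it is possible that the improved clinical services may attract a greater number of patients to MOH care than anticipated". The split of patients across facilities is not given.

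Section 6.2 makes the clinical outcomes secondary. They are pilot data for Ministry of Health stakeholders and a rehearsal of procedures, not a test of effectiveness.

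**The concern.** In a model with a facility random effect, the precision of an overall mean or proportion depends partly on the between-facility variance. Here that variance is estimated from 11 units. Maximum likelihood tends to underestimate it with so few, and a normal critical value ignores the error in estimating it. Both faults shorten the interval. REML corrects the first but not the second. Enrolling more patients does not help, because the number of facilities stays at 11.

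At stake is how certain the secondary clinical estimates appear, chiefly mean systolic and diastolic pressure and the control proportions. Section 12 says the investigators and stakeholders will use the results in planning scale-up. An honest statement of uncertainty is one of the main things a pilot of this kind can offer.

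**Working it through.** **Inputs from the documents.** Facilities: 2 + 9 = 11, as stated. Patients: 45 + 45 + 10 = 100, as stated. Per condition: 45 + 10 = 55 with hypertension and 45 + 10 = 55 with diabetes, or 55 / 11 = 5 per facility on average. The plan gives no power, confidence level, ICC, standard deviation or interval width to reproduce.

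**Assumptions, not in the documents.** Two-sided 95% intervals. Facility ICC from 0 to 0.20. Facility sizes per condition either equal (5 each) or unequal (14, 14 and nine of 3, total 55). For larger enrolment, ten times the unequal sizes (total 550). True proportion 0.40 in the logistic model.

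**Closed form, equal facilities, between-facility variation dominating.** The correct reference for the overall mean is t on 11 − 1 = 10 df.

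- Critical values: t = 2.228 and z = 1.960. The normal interval has 1.960 / 2.228 = 0.88 of the right width, 12% too narrow.
- Coverage with the unbiased variance: P(|t₁₀| < 1.960) = 92.2%.
- Coverage with the ML variance, smaller by a factor 10/11: P(|t₁₀| < 1.960 × √(10/11)) = P(|t₁₀| < 1.869) = 90.9%.

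**Simulation, linear random-intercept model, overall mean, normal-based interval, 55 patients (2,000 runs per scenario).**

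| ICC | Equal, ML | Equal, REML | Unequal, ML | Unequal, REML |
|---|---|---|---|---|
| 0 | 95.9% | 96.3% | 94.9% | 95.7% |
| 0.02 | 95.1% | 95.4% | 93.6% | 94.2% |
| 0.05 | 94.1% | 94.7% | 91.8% | 92.7% |
| 0.10 | 93.1% | 94.0% | 91.0% | 92.0% |
| 0.20 | 91.8% | 92.9% | 89.1% | 90.6% |

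With 550 patients in unequal facilities and an ICC of 0.02 or more, ML covers about 89–91% and REML about 91–92%.

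**Simulation, logistic random-intercept model, unequal sizes (ML, 800 runs per scenario).**

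| ICC | 55 patients, z | 55 patients, t(10) | 550 patients, z | 550 patients, t(10) |
|---|---|---|---|---|
| 0.02 | 96.3% | 98.4% | 90.2% | 93.6% |
| 0.05 | 96.4% | 98.0% | 92.5% | 94.9% |
| 0.10 | 94.5% | 96.4% | 90.7% | 93.4% |
| 0.20 | 93.0% | 96.4% | 90.1% | 93.8% |

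**With the correction.** REML with t on 10 df covers an overall mean 94–98% of the time in all linear scenarios. The width ratio is 2.228 / 1.960 = 1.137, about 14% wider.

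**Before-after change with a facility intercept only (ML, z, 1,500 runs, ICC 0.05 or 0.10, facility-by-time variance 0 to 0.05).** Coverage is 92–95% with no between-patient variance. It is 96–100% when 40–60% of the variance lies between patients, because the fitted model has no patient level.

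Simulation error is about 0.5 to 1 percentage point.

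**The case against.** The strongest reply is that the plan leaves the interval method unstated, so nothing in it is shown to be wrong. Four stronger readings are tempting, and the documents do not support them.

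- **That the plan uses large-sample inference.** Section 9 names models and software only. Normal-based intervals are a condition of the figures above, not a stated choice.
- **That intervals will be too narrow in general.** Facility sizes and ICC are not given. With equal sizes and an ICC of 0.02 or less, coverage is nominal. The logistic model at 55 patients is near nominal up to an ICC of 0.10. For within-patient change, a model with facility as its only level can err the other way and give intervals that are too wide.
- **That a comparison of the two districts would reject falsely too often.** Section 9 plans no such contrast and no hypothesis test of a clinical outcome, so there is no planned error rate to inflate.
- **That the pilot's main conclusions are at risk.** The benchmarks in Table 2 are questionnaire medians, enrolment counts and a follow-up proportion set against fixed values. None is tied to these models, and questionnaire data are to be analysed descriptively.

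All four limits stand. What remains is that the plan commits to a clustered model on 11 units, and ordinary normal-based output from that model understates uncertainty for overall means at moderate ICC. Larger enrolment, which section 8 foresees, extends this to low ICC and to proportions. An extension to 12 months, which section 10.2 allows, would still leave 11 facilities.

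**Conclusion.** The point holds conditionally. If normal-based intervals are used, nominal 95% intervals for an overall mean cover about 89–94% at 55 patients per condition and an ICC of 0.05–0.20, depending on how unequal the facilities are. At an assumed 550 patients the figures are about 89–91% for the linear model by ML (ICC 0.02 or more) and 90–93% for the logistic model. They rest on assumed ICCs, facility sizes and a 95% level.

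This is more than a missing detail, because a known and better method exists for this number of clusters. It is still modest in consequence, since only secondary clinical outcomes in a single-arm pilot are affected. It is worth correcting before analysis, and it is not a threat to the primary assessment.

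**What to change.** Add to section 9:

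> Linear models will be fitted by REML with Kenward-Roger (or Satterthwaite) degrees of freedom. In logistic models, intervals for overall proportions and facility-level terms will use a t reference with degrees of freedom based on the number of facilities (10 for an overall estimate).

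Two limits belong with it. Facility-count degrees of freedom should not be applied to patient-level covariates such as age, sex or education, where they would widen intervals needlessly. Where repeated visits are modelled, include a patient-level random effect. The section should also state which quantity each model estimates (level at a time point, or change).

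The cost is a short addition to the text and a change of software options. Intervals for an overall estimate become about 14% wider. For proportions at the planned size the t reference is somewhat conservative (96–98% coverage in the simulation). The linear correction checked was REML with t on 10 df; Kenward-Roger itself was not simulated.

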5.4.5. Systems monitoring and feedback of key indicators

HEARTS requires the use of routine administrative clinical data to monitor key indicators and to iteratively improve the quality of hypertension and diabetes care.³⁷ Each month, we will present aggregate reports of key indicators using data drawn from DHIS2 to MOH stakeholders at the health district (i.e., municipal) and health area (i.e., departmental) levels. The key indicators will be the same as the HEARTS-aligned secondary outcomes described below. We will use a suite of DHIS2 visualization tools built by PAHO, including maps, graphs, and dashboards. In the WHO classification system for digital health interventions, this intervention component is a health system manager intervention focusing on facility management.³⁶ Facility-level monitoring using DHIS2 will be complemented by ongoing health worker training (5.3.1) and site supervision visits (5.3.4).

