6. OUTCOMES

6.1. Primary outcomes

Primary outcomes will be feasibility and acceptability as defined in the Implementation Outcomes Framework (**Table 2**).³⁸ These outcomes will be assessed using quantitative data, qualitative data, and mixed methods (integrated qualitative and quantitative data). Given the study team's prior experience with HEARTS-aligned projects, the focus of the feasibility and acceptability assessments will be on integrating diabetes into the HEARTS model.

Feasibility is the extent to which a new intervention can be successfully carried out in an organization.³⁸ Among MOH participants, feasibility will be assessed through the four-item Feasibility of Intervention Measure (FIM) questionnaire³⁹ and semi-structured interviews. Among patient participants, feasibility will be assessed using enrollment data.

Acceptability is the stakeholders' perception that a new intervention is agreeable or satisfactory.³⁸ Among MOH participants, acceptability will be assessed using the Acceptability of Intervention Measure (AIM) questionnaire³⁹ and semi-structured interviews. Among patient participants, acceptability will be assessed using follow-up visit data and semi-structured interviews.

Table 2: Measures of feasibility and acceptability and their benchmarks

Measure	Minimum benchmark
Feasibility	
Feasibility questionnaire (FIM) among MOH participants	Median $\geq 3.5^a$
Reasons for perceptions of feasibility/infeasibility	N/A
Number of patient participants with diabetes enrolled per health district ^b	25
Number of patient participants with hypertension enrolled per health district ^b	25
Acceptability	
Acceptability questionnaire (AIM) among MOH participants	Median $\geq 3.5^a$

Table 2: Measures of feasibility and acceptability and their benchmarks

Measure	Minimum benchmark
Proportion of patient participants with subsequent follow-up visit within 3 months (among those enrolled with ≥ 3 months remaining in pilot)	75%
Reasons for perceptions of acceptability/infeasibility among patient and MOH participants	N/A
Reasons for dropouts among patient participants	N/A

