Primary outcomes in this pilot study are feasibility and acceptability as defined in the Implementation Outcomes Framework. ^a The FIM and AIM scales range from 1 to 5 with higher values implying greater feasibility or acceptability, respectively; scores are averaged within each participant. ^b Enrollment is defined by a patient having at least one clinic visit entered in the DHIS2 or equivalent longitudinal medical record system; a given patient may have both diabetes and hypertension and thus count toward each benchmark. Abbreviations: AIM: Acceptability of Intervention Measure; FIM: Feasibility of Intervention Measure; MOH: Ministry of Health.	

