6.2. Secondary outcomes

Secondary outcomes include clinical outcomes, implementation outcomes, and patient-related outcome measures (**Table 3**).

Clinical effectiveness outcomes are based on recommended HEARTS monitoring indicators.^{37,40} Clinical outcomes are assessed to provide pilot data to key MOH stakeholders and to rehearse study procedures rather than to evaluate effectiveness.

Implementation outcomes³⁸ will assess facility-level adoption and the fidelity of implementation of each intervention component.

Patient-related outcomes measures relating to diabetes will be conducted to translate and validate questionnaires in Guatemalan Spanish and Mayan Kaqchikel. Measures include diabetes distress, quality of life, and self-care assessments. We will use validated Spanish or professionally translated Mayan language versions of each instrument. These assessments are exploratory to refine the study team's use of these instruments in rural Guatemala.

Table 3: Outcomes and data sources

Outcome	Description and data sources
Primary outcomes	
Feasibility	FIM questionnaires and MOH data from DHIS2 (quantitative); semi-structured interviews with MOH participants (qualitative)
Acceptability	AIM questionnaires and MOH data from DHIS2 (quantitative); semi-structured interviews with patient and MOH participants (qualitative)
Secondary outcomes	
Clinical outcomes	

Table 3: Outcomes and data sources

Outcome	Description and data sources
Number of patients receiving hypertension medication treatment per month (“hypertension treatment rate”)	MOH data from SIGSA (quantitative)
Number of patients receiving diabetes medication treatment per month (“diabetes treatment rate”)	MOH data from SIGSA (quantitative)
Proportion achieving glycemic control (FBG <115 mg/dl or RBG <160 mg/dl) among patients with diabetes	MOH data from DHIS2 (quantitative)
Proportion achieving control of blood pressure (<130/80 mmHg) among patients with hypertension	MOH data from DHIS2 (quantitative)
Mean SBP and DBP among patients with hypertension	MOH data from DHIS2 (quantitative)
Implementation outcomes	
Adoption	Number of participating health facilities, defined as having enrolled at least one patient with hypertension or diabetes (quantitative); reasons for variation (qualitative)

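### Do the clinical outcomes need a stated visit, and the clinical models a patient-level term, before this pilot can be analysed?

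*Combined protocol and SAP*

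**What the plan says.** The quantitative paragraph of Section 9 specifies "multilevel linear and logistic regression models of individual-level data adjusting for clustering of participants within primary health facilities". Facility is the only source of clustering it names. It gives no time term, comparison or significance level for the clinical data, and says sociodemographic covariates may be explored if numbers allow.

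The outcomes are in Section 6.2, Table 3. A typical row is "Proportion achieving control of blood pressure (<130/80 mmHg) among patients with hypertension". The glycemic row names the type of glucose test and its cut-offs, and a further row lists mean SBP and DBP. The two treatment-rate rows are counted per month. The three control and mean rows carry no visit or time window.

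Other sections show that many patients will have more than one record. Section 8 chooses interviewees by "low versus high retention levels (defined by number of clinical visits within the study time period"), and Table 2 sets a 75% benchmark for "Proportion of patient participants with subsequent follow-up visit within 3 months (among those enrolled with ≥ 3 months remaining in pilot"). A single visit is enough to enter the study: "Enrollment is defined by a patient having at least one clinic visit entered in the DHIS2" or an equivalent record.

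Two statements frame the purpose. Section 6.2 says "Clinical effectiveness outcomes are based on recommended HEARTS monitoring indicators", citing sources outside the protocol, and then: "Clinical outcomes are assessed to provide pilot data to key MOH stakeholders and to rehearse study procedures rather than to evaluate effectiveness". Section 5.4.5 adds a reporting use: "Each month, we will present aggregate reports of key indicators using data drawn from DHIS2 to MOH stakeholders".

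**The concern.** A model with only a facility intercept, fitted to every visit, treats one patient's readings as independent given the facility. Standard errors for age, sex or education would then be too small.

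If instead one record per patient is used, someone must choose it. Enrollment runs through the six months and needs only one visit, so late enrollees and patients who do not return have only an entry reading, while others have a follow-up reading. Table 2 protects its retention measure by requiring at least three months remaining; Table 3 has no such limit. Newly diagnosed hypertensive patients qualify under Section 5.3.1 with an average at or above 130 systolic or 80 diastolic, which Table 3 counts as uncontrolled. The control rate given to the Ministry could therefore depend partly on when patients joined and whether they came back.

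**Working it through.** The documents contain no power, precision or error-rate figure for these outcomes, so there is nothing of the plan's own to reproduce. The check asks what each reading of the plan would do.

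**Inputs from the documents.** Section 8: 45 patients with hypertension only, 45 with diabetes only, 10 with both, so 45 + 10 = 55 per condition. Eleven facilities, 55/11 = 5 patients each on average. Six months' duration; 75% return benchmark.

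**Assumed inputs.** Visits per patient (m), share of variance lying between patients (ρ), accrual pattern, and control rates. None is in the documents.

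**1. One record per patient.** Participants nested in facilities is then the whole structure, and the stated model fits it. No within-patient correlation arises.

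**2. All visits, facility term only.** For a patient-level covariate the variance is understated by about 1 + (m − 1)ρ, and the false-positive rate of a nominal 5% test is about 2 × [1 − Φ(1.96/√(1 + (m − 1)ρ))].

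| m | ρ = 1/3 | ρ = 1/2 |
|---|---|---|
| 2 | factor 1.33, 9.0% | factor 1.50, 11.0% |
| 4 | factor 2.00, 16.6% | factor 2.50, 21.5% |
| 6 | factor 2.67, 23.0% | factor 3.50, 29.5% |

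Simulation of the linear model (55 patients, 11 facilities, REML, z-test, 2,000 runs per setting) agrees closely: 9.6% and 12.4% at two visits, 16.9% and 22.9% at four, 25.9% and 32.1% at six. With a participant intercept the rate is 5.7–6.4%. The logistic model behaves alike but more mildly: 6–8%, 13–17% and 18–28%.

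The overall mean fares much better. With one to six visits per patient and unequal facilities, 95% interval coverage is 91–94% with the facility term alone and 94–95% with the participant term added, because the facility intercept absorbs much of the patient variation. The effect on time trends is not uniform. In linear runs the facility-only standard error is too large, by a ratio of 1.11 to 1.37; in logistic runs with unequal visits the two models show no clear difference.

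**3. One record per patient, entry and follow-up mixed.** Assume uniform accrual, last-month enrollees with an entry reading only, 25% non-return among those with at least three months left, and return by everyone enrolled in months four and five:

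- entry-only share = 1/6 + 0.25 × 3/6 = 29.2%, or 9.2 + 6.9 = 16.0 of 55;
- reported rate = 0.50 − 0.292 × (0.50 − entry control);
- entry control 20%: 0.50 − 0.292 × 0.30 = 41%; entry control 50%: 50%, no shift.

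Front-loaded accrual gives 13–14 entry-only patients. If everyone with time to return does so, the number is 9 under uniform accrual and lower if accrual is front-loaded.

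**4. Precision.** The 95% half-width at 50% is 1.96 × √(0.25/55) = 13.2 points. Restricting to 55 − 16 = 39 patients with follow-up gives 1.96 × √(0.25/39) = 15.7 points.

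**5. Choice of reading.** With an assumed systolic mean of 138, SD 18, three visits, correlation 0.5 and no trend, the share below 130 is about 33% on a single reading and 29% on the patient's mean. Only unusual rules move it far: 57% if any reading counts, 12% if all must.

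**The case for a change.** The strongest case for a change is that neither reading of Section 9 is complete. If all visits enter, the stated clustering is insufficient for the covariates the plan says may be explored. If one record enters, the outcome is undefined. A pilot meant to supply data to the Ministry and to rehearse procedures is poorly served by an indicator without a time frame, especially as the same indicators are reported monthly and the treatment-rate rows do have a period. A few sentences would settle it.

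Much of this stands as description: the text does not name the visit. It does not show that any stated rule gives a wrong answer. The all-visits, facility-only model is only one reading. The sentence fits one record per patient, and it can also describe the upper levels of visits within participants within facilities, where the patient term is already present. The direction of bias is not fixed either. The entry threshold binds only newly diagnosed patients; previously diagnosed patients are eligible too, and both districts had earlier hypertension projects, so entry control could be close to follow-up control. The cited HEARTS indicators and the DHIS2 visit forms listed in Section 15 were not available here and may already define the reading.

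The obvious repairs also have costs. Using the last visit after enrollment would still leave timing dependent on accrual. A participant intercept nested in facility needs a rule for patients whose care is shared between health post and health center under Section 5.4.2. In simulated three-level logistic fits, the facility variance was estimated at zero in 47–59% of runs.

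**Conclusion.** No change to the plan follows. This is missing detail on secondary outcomes that analysts would fill sensibly, by choosing and reporting a reading and by allowing for repeated measurements if they model more than one visit per patient.

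The largest figures, false-positive rates of 17–22% at four visits and higher at six, apply only if all visits enter, nothing represents the patient, and someone tests a patient-level covariate. The plan commits to none of these together. The possible shift in a reported control rate, from none to about 9 points, rests on assumed accrual, return and entry control, and lies within the 13-point half-width that 55 patients give in any case. Ordinary choices of reading differ by about 4 points in the illustration. The documents establish neither the size nor the direction of any shift.

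The questionnaire benchmarks, enrollment counts and follow-up proportion in Table 2 use none of these models, so the conclusions on feasibility and acceptability are unaffected. The judgement would differ if the clinical outcomes were to support an effectiveness claim, which Section 6.2 rules out.
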